Cover Page

Title: Adhesive Tape Placement on Patients' Masks in the ED Increases Compliance of Proper Face Mask Use

[name]

11/9/2021

NCT04812184

Protocol ID IUMASKstudy

Study Design and Setting:

This study was an open-label randomized control trial at Eskenazi Hospital ED from April 2020 to October 2020. Eskenazi Hospital is a busy, urban, academic, level 1 trauma center in downtown Indianapolis serving a racially diverse, underserved population with over 100,000 annual ED visits. This study was approved by the Indiana University Institutional Review Board (protocol #2004425945) and registered on ClinicalTrials.gov (NCT04812184).

Selection of Participants:

Patients presenting to the ED were screened for enrollment by trained research personnel when one of the study authors was working. All patients in the ED were required to wear facial coverings by institutional policy, and patient-provided personal masks were acceptable. Patients were excluded if they were: (1) pregnant; (2) prisoners; (3) not English- or Spanish-speaking; (4) intoxicated or with decompensated psychiatric illness; (5) presenting to the ED with a life-threatening condition; (6) allergic to standard tape and/or tegaderm. Patients were approached and verbal consent was obtained in their private ED room, then participants were randomized to either the control or intervention arms by simple randomization.

Randomization:

The randomization sequence was generated by a computerized random number generator (simple randomization). The randomization assignment was concealed from the study team and was provided within our REDCap database only after participants had been enrolled and provided informed consent.

Interventions:

Participants in the intervention arm had standard surgical tape placed over the bridge of the nose to adhere to the top of the mask (Supplemental Figure 1). Control participants had no intervention. Participants were told the study was about PPE use, but no additional instruction was given to participants regarding proper mask use, nor were reminders made by the research staff on proper mask use. No blinding was used in this study.

Sample Size:

Assuming 50% baseline proper mask use, 58 participants per arm were needed to have 80% power to detect a 25% relative difference in proper mask adherence assuming a two-sided chi-square test and alpha = 0.05.

Measurements:

At time of consent, a researcher assessed participants for their mask type, age, gender, race, ethnicity, Charlson Comorbidity Index (CCI)⁸, and chief complaint, which were then entered into a REDCap database. After randomization, the participants were reevaluated at 60 minutes by the same researcher, and the mask location (correct placement, on chin, nose exposed, mask removed, nose/mouth exposed) and patient disposition (admission/discharge) were recorded (Supplemental Figure 1). Participants were reevaluated without notice and were blinded as to why the investigator was entering the room.

Outcomes:

The primary outcome of this trial was proper mask utilization at 60 minutes assessed by a researcher. A subgroup analysis was performed comparing the frequency of correct mask wearing by mask type (hospital-provided versus patient-supplied masks).

Analysis:

Patient demographics and characteristics were compared between the control and treatment groups (self-reported) to ensure balance after randomization. To test for differences between groups on outcomes, Microsoft Excel (Microsoft Corporation, Redmond, WA) was used, and the Chi-square test (or Fisher's exact test for <5 counts) was used for categorical variables and the Wilcoxon test for continuous variables. All analyses were conducted by intention-to-treat.

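### 58 per arm gives about 27% power, not 80%, for a 25% relative difference from 50%; the number fits only a 25 percentage-point absolute difference

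*Combined protocol and SAP*

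**What the plan says.** The whole calculation is one sentence in the Sample Size section of the combined protocol and SAP. It sets the control rate ("Assuming 50% baseline proper mask use"), the number, power and target effect ("58 participants per arm were needed to have 80% power to detect a 25% relative difference in proper mask adherence") and the test ("assuming a two-sided chi-square test and alpha = 0.05").

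The Outcomes section makes the endpoint binary: "The primary outcome of this trial was proper mask utilization at 60 minutes assessed by a researcher". The Analysis section names the chi-square test for categorical variables, in line with the sample-size assumption.

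The document gives no target rate for the tape arm, no absolute difference and no allowance for dropout. The word relative is therefore all the reader has for interpreting the 25%.

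**The concern.** A relative difference of 25% from a 50% baseline is only 12.5 percentage points. At rates near 50%, where binomial variance is largest, 58 per arm is far too few to detect 12.5 points with 80% power.

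What is at stake is how the result is read. A reader who trusts the sentence would think that a true 12.5-point improvement had only a 20% chance of being missed, and would take a non-significant result as fair evidence against it. On the stated inputs the chance of missing it is about 73%. Whatever the result, the sentence understates by half the effect for which the trial has 80% power, and anyone sizing a similar study from it would enrol too few people.

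**Working it through.** **Inputs, all from the Sample Size section:** control rate p1 = 0.50; two-sided alpha 0.05 (z = 1.960); power 80% (z = 0.842); n = 58 per arm; equal arms; chi-square test on two proportions.

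**Formula.** With d = |p2 − p1| and p̄ = (p1 + p2)/2, let A = √[2p̄(1 − p̄)] and B = √[p1(1 − p1) + p2(1 − p2)]. Then

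n per arm = (1.960·A + 0.842·B)² / d²

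power at n per arm = Φ[(d·√n − 1.960·A) / B]

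**Step 1: find the effect that reproduces 58.** Take p2 = 0.75, so d = 0.25 and p̄ = 0.625.
- A = √0.46875 = 0.6847; B = √0.4375 = 0.6614.
- n = (1.3419 + 0.5567)² / 0.0625 = 57.7, so **58 per arm**.
- Power at 58 = Φ[(0.25 × 7.616 − 1.3419) / 0.6614] = Φ(0.850) = **80.2%**.

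The plan's figures are recovered, but for 25 percentage points absolute, which is a 50% relative increase (0.75/0.50 = 1.5). A fall to 25% gives the same n and power by symmetry.

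**Step 2: use the effect as written.** A 25% relative increase is p2 = 0.50 × 1.25 = 0.625, so d = 0.125 and p̄ = 0.5625.
- A = √0.4921875 = 0.7016; B = √0.484375 = 0.6960.
- n = (1.3750 + 0.5857)² / 0.015625 = 246.1, so **247 per arm** (494 in total, against 2 × 58 = 116).
- Power at 58 = Φ[(0.125 × 7.616 − 1.3750) / 0.6960] = Φ(−0.608) = **27.2%**.

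A 25% relative decrease (p2 = 0.375) gives the same 247 and 27.2%.

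**Step 3: check by exact enumeration.** Summing binomial probabilities over all outcomes with 58 per arm, the power of the chi-square test is:

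| True rates | No continuity correction | Yates correction |
|---|---|---|
| 50% vs 62.5% | 27.2% | 21.3% |
| 50% vs 75% | 79.9% | 74.3% |

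**Step 4: look for another reading that rescues the sentence.**

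| Reading | n per arm for 80% power |
|---|---|
| 50% vs 62.5%, unpooled variance (243.3) | 244 |
| 50% vs 62.5%, arcsine (245.9) | 246 |
| 50% vs 62.5%, continuity-corrected | 262 |
| 50% vs 62.5%, one-sided 0.05 | 194 |
| 50% is 0.75 times the other arm (p2 = 66.7%) | 137 |
| 50% is 1.25 times the other arm (p2 = 40%) | 388 |

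None is near 58. Treating 58 as half of each arm (116 per arm) still gives only 48.4% power for 50% versus 62.5%. Solving for the smallest increase detectable with 80% power at 58 per arm gives p2 = 74.9%, about 25 points.

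**The case against.** The best counter-argument is that this is one wrong word. The number, power, test and alpha agree with one another if the 25% means percentage points. On that reading the sample size was calculated correctly, and 27% describes an effect for which the trial was never sized. The study ran from April to October 2020, so no wording change can alter enrolment. Neither the endpoint nor the analysis depends on the word, and the practical harm arises mainly if the result is non-significant.

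Much of this is fair. A wording slip is the likeliest cause, and nothing here shows that the calculation itself was botched. But the document never states the intended target rate, so a reader cannot recover 50% versus 75% without redoing the arithmetic. The word also sits in the only power statement for the primary outcome and changes its truth by about 53 percentage points of power (80% against 27%).

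A further point stands and limits what should be said about a null result. What a result excludes depends on its confidence interval, not on planned power. With 58 per arm and rates near 50%, the 95% half-width is about 1.96 × √(0.5/58) = 18.2 points. A non-significant result with an observed difference of about −6 points or lower would therefore exclude a 12.5-point benefit. By enumeration, with both true rates at 50%, about 25% of non-significant results would do so. The accurate claim is that non-significance does not by itself rule out an effect of that size.

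**Conclusion.** The concern holds. On the document's own inputs, 58 per arm has about 27% power for a 25% relative difference from 50%. Eighty percent power for that effect would need 247 per arm, about 4.3 times as many (247/58). The stated number is correct only for a 25 percentage-point absolute difference, twice the effect named.

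This rests on equal arms and complete outcome data. Simple randomization may leave the arms slightly unequal, which would lower power marginally and changes nothing here. Which effect the authors intended is not known from the document. The sentence is false under either intention, because it joins a relative effect to a number that matches an absolute one.

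**What to change.** Replace the Sample Size sentence with wording such as: *With 50% proper mask use in the control arm, 58 participants per arm give 80% power to detect a 25 percentage-point absolute difference (for example 50% versus 75%, a 50% relative increase), two-sided chi-square test, alpha = 0.05.* This is true whatever was originally intended.

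Add: *Power for a 25% relative difference (50% versus 62.5%) is about 27%, so a non-significant result does not by itself rule out an effect of that size.*

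The authors should also confirm which effect they planned for. If it was the relative one, the document should say that the trial was planned at about a quarter of the size needed (58 against 247 per arm).

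The cost is one or two sentences and a less favourable statement of what the trial could detect. No participants, endpoint or analysis change.

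### Does the mask-type subgroup analysis need rewriting because it does not say how trial arm enters?

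*Combined protocol and SAP*

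**What the plan says.** The Outcomes section first fixes the primary endpoint: "The primary outcome of this trial was proper mask utilization at 60 minutes assessed by a researcher". It then adds the secondary comparison: "A subgroup analysis was performed comparing the frequency of correct mask wearing by mask type (hospital-provided versus patient-supplied masks". Trial arm does not appear in that sentence.

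The Analysis section gives the only method text. Its opening sentence speaks of comparing the control and treatment groups at baseline. The next begins "To test for differences between groups on outcomes" and states that "the Chi-square test (or Fisher's exact test for <5 counts) was used for categorical variables and the Wilcoxon test for continuous variables". It mentions no stratified test, model or interaction term.

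Three other statements bear on the point:

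- Measurements: "At time of consent, a researcher assessed participants for their mask type".
- Selection of Participants: "patient-provided personal masks were acceptable", so mask type was not assigned by the trial.
- Selection of Participants: "participants were randomized to either the control or intervention arms by simple randomization", with no stratification by mask type.

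**The concern.** In a randomised trial, the term subgroup analysis usually means the treatment effect within subgroups. The sentence here describes something else, a comparison between mask types, and leaves the role of arm open. The possible analyses support different statements. A comparison of mask types sets patients who brought a mask against those who did not, and any difference may reflect who those patients are. A comparison of tape with control within each type is randomised.

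If the within-type comparison was meant, the listed tests yield two p-values and nothing that tests whether the two tape effects differ. A reader could see one significant and one non-significant result and conclude that tape works with one kind of mask only. What is at stake is the interpretation of a secondary result.

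**Working it through.** **Inputs.** From the document: 50% baseline, 58 per arm, 80% power and two-sided alpha 0.05 (Sample Size); simple randomisation (Selection of Participants, Randomization); chi-square, or Fisher for small counts (Analysis). Not in the document, so assumed: 116 analysed (2 × 58), the mask-type totals shown below, and, in step 4, the same true tape effect in both types.

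**Step 1. The plan's own figure.** Sample Size states that "58 participants per arm were needed to have 80% power to detect a 25% relative difference in proper mask adherence". The usual formula is n = [1.96√(2p̄(1−p̄)) + 0.8416√(p₁(1−p₁)+p₂(1−p₂))]² / (p₂−p₁)².

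- 50% vs 75%: (1.96×0.6847 + 0.8416×0.6614)² / 0.25² = 1.8986² / 0.0625 = 57.7, so 58.
- 50% vs 62.5%: (1.96×0.7016 + 0.8416×0.6960)² / 0.125² = 1.9608² / 0.015625 = 246.1, so 247.

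The stated 58 therefore fits 25 percentage points rather than a 25% relative difference. That is a separate matter; step 4 uses both effects.

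**Step 2. The possible readings.**

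1. Mask types compared with arms pooled: observational.
2. Mask types compared within each arm: also observational.
3. Tape vs control within each mask type: randomised, on a factor recorded at consent, before assignment was revealed.

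The literal wording fits 1 or 2. The Analysis section's mention of groups, coming straight after the two arms are named, leans towards 3. None of the three is an invalid analysis in itself.

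**Step 3. Would pooling the arms spoil the literal reading?** No. Tape was randomised, so half of each mask type is expected to have it. The chance difference in tape share between types has standard deviation √(0.25/N₁ + 0.25/N₂). Multiplied by a 25-point tape effect, this shifts the mask-type comparison by:

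- 58/58: 0.0928 × 25 = 2.3 points
- 88/28: 0.1085 × 25 = 2.7 points

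The standard error of the mask-type difference at 62.5% overall (midway between 50% and 75%) is √(0.625×0.375×(1/N₁+1/N₂)), or 9.0 and 10.5 points. Chance imbalance in tape is minor beside it and does not favour either type.

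**Step 4. The third reading.** With 29 per arm in each type, power at 50% vs 75% is 0.503 per test, so exactly one test is significant with probability 2 × 0.503 × 0.497 = 0.500. Exact binomial enumeration, with arm sizes random within type and the plan's chi-square/Fisher rule, gives:

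| Assumed mask-type totals | Exactly one significant, 50% vs 75% | Exactly one significant, 50% vs 62.5% | Neither significant, 50% vs 62.5% |
|---|---|---|---|
| 58/58 | 50.0% | 26.9% | 70.5% |
| 80/36 | 55.9% | 27.3% | 70.4% |
| 88/28 | 61.6% | 24.9% | 73.8% |

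Under the same assumptions, a 95% hybrid-score interval for the difference between the two tape effects excludes zero in 5% to 6% of simulated trials. Contrasting two p-values would mislead; the document does not do so.

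**Step 5. What an interaction estimate would add.** With 50% vs 75% in both types and a share s of hospital masks, SE = √(0.4375/(58s) + 0.4375/(58(1−s))), where 0.4375 = 0.25 + 0.1875. At s = 0.5 this is √(0.4375/29 + 0.4375/29) = 0.174, and 1.96 × 0.174 = 0.34.

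| Assumed hospital-mask share | 95% half-width (points) | Power for a 25-point interaction |
|---|---|---|
| 50% | 34 | 30% |
| 70% | 37 | 26% |
| 80% | 43 | 21% |
| 90% | 57 | 14% |

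**The case for a change.** The strongest case for a change is that it costs one phrase. The label invites a reading about tape effects, the nearest mention of groups points to the arms, and step 4 shows that a split pair of p-values would be common even with no true difference in effect. An interval for the interaction, however wide, is a better basis for inference than two p-values.

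Part of this stands. The document does not settle which comparison was made, and a reader should draw no conclusion about tape by mask type from either observational version, or from two p-values set side by side.

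The rest does not carry. Every figure in step 4 belongs to a reading the sentence does not state and depends on mask-type totals the document does not give. The document neither asserts nor tests effect modification, so an interaction analysis would answer a question it does not pose, usually without a conclusion. The text is also a past-tense account dated 11/9/2021 of a trial run from April to October 2020, so only the reporting could still alter. A table of the subgroup result would show at once whether it is split by arm.

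**Conclusion.** No change follows. The sentence omits a detail that the analyst knows and that presentation of the result would make plain. On its literal reading the analysis is legitimate, and pooling the arms adds only about 2 to 3 points of unsystematic chance imbalance, given a 25-point tape effect and the assumed splits. The randomised primary comparison at 60 minutes is unaffected on any reading.

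The potential misreading is sizeable only if within-type p-values are contrasted: 50% to 62% of trials would show a split result at 50% vs 75%, and 25% to 27% at 50% vs 62.5%. These figures assume 116 analysed, 50% correct wearing in control, equal tape effects in both types and the mask-type totals shown. If a report were to discuss tape effects by mask type, an exploratory difference in risk differences with its interval would be the suitable summary; nothing in this document raises that discussion.

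### Comparing the arms after simple randomisation cannot ensure balance, and mask type, recorded at consent, is left out of the primary comparison

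*Combined protocol and SAP*

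**What the plan says.** The Analysis section gives the purpose of the baseline comparison: "Patient demographics and characteristics were compared between the control and treatment groups (self-reported) to ensure balance after randomization". Selection of Participants states that "participants were randomized to either the control or intervention arms by simple randomization", and the Randomization section repeats the method: "The randomization sequence was generated by a computerized random number generator (simple randomization". No blocking, stratification or minimisation is described.

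Measurements lists seven items recorded at consent: mask type, age, gender, race, ethnicity, comorbidity index and chief complaint. Outcomes uses mask type (hospital-provided or patient-supplied) for the one named subgroup analysis. Analysis describes no adjusted or stratified comparison of the arms.

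The tests in Analysis are introduced for outcomes. They include "the Wilcoxon test for continuous variables", although no continuous outcome is defined. Sample Size states that "58 participants per arm were needed to have 80% power".

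**The concern.** The wording credits the design with a property it lacks. Once allocation is done, a table or a test can show how the arms turned out but cannot change it. Because allocation was computer-generated and concealed, any baseline difference arises by chance, so a baseline p-value tests a null hypothesis already known to be true. In a trial of this size a non-significant p-value does not show balance either. The plan does not say what follows if an imbalance is seen.

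Mask type matters most here because the tape is stuck to the mask and the plan itself singles the factor out. If mask type predicts proper wear, a chance excess of one type in the tape arm moves the observed difference, and the plan gives the reader no stratified estimate to set beside it. Precision is also lost by ignoring a predictor that was already collected.

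**Working it through.** **Inputs.** From Sample Size: 50% baseline proper use, 58 per arm, 80% power, two-sided chi-square test, alpha 0.05. Total taken as 2 × 58 = 116; the number actually enrolled is not given. A 1:1 ratio is assumed, as equal arm sizes imply. Assumed because the documents give neither figure: share of hospital-provided masks 30% to 50%; gap in proper wear between mask types 20 to 40 points.

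**1. The plan's own figure.** n = [1.96 √(2p̄(1−p̄)) + 0.842 √(p₁(1−p₁) + p₂(1−p₂))]² / (p₁−p₂)².
- 50% v 75%: (1.342 + 0.557)² / 0.0625 = 57.7, so 58 per arm, power 80.2%.
- 50% v 62.5%, the literal meaning of "detect a 25% relative difference in proper mask adherence": (1.375 + 0.586)² / 0.015625 = 246.1, so 247 per arm; 58 per arm has 27% power.

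So 58 fits only an absolute 25-point difference. That is a separate and more serious problem. Here it only fixes N = 116 and the contrast used in step 6.

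**2. Arm sizes.** Under Binomial(116, 0.5), an exact 58/58 split has probability 7.4%, and the arms differ by 12 or more in 31% of trials. At 50/66 power is 79.8% against 80.2%, so unequal arm size costs almost nothing.

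**3. Chance imbalance in mask type.** The standard error of the difference in share is √(q(1−q) × 2/58): 9.3 points at q = 0.5 and 8.5 at q = 0.3. Ten points is therefore 1.08 or 1.18 standard errors. Simulation with random arm sizes (1,000,000 trials per setting) gives:

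| Imbalance | Share 30% | Share 50% |
|---|---|---|
| 10 points or more | 24% | 29% |
| 15 points or more | 8% | 11% |
| 20 points or more | 1.9% | 3.2% |

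**4. What a 5% baseline test would flag.** At 58/58, p < 0.05 needs a difference of about 1.96 × 8.5 = 16.7 points (share 30%) or 1.96 × 9.3 = 18.2 points (share 50%). The test flags about 5% of all trials. The proportion flagged among imbalances of 10 points or more is then 0.051/0.243 = 21% (share 30%) or 0.051/0.292 = 17% (share 50%). At 15 points or more it is 64% and 46%; at 20 or more, essentially 100%.

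**5. Effect on the primary result.** Shift = imbalance × gap. A 10-point imbalance with a gap of 20 to 40 points moves the arm difference by 2 to 4 points. The standard error of that difference is √((0.25 + 0.1875)/58) = 8.7 points. Simulated type I error of the unadjusted test is about 5.1% overall. Given an imbalance of 10 points or more it is 5.9%, 6.9% and 8.1% for gaps of 20, 30 and 40 points.

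**6. What stratifying gains.** Simulated power on 50% v 75%, with the same gap in both arms (300,000 trials per setting; Cochran-Mantel-Haenszel without continuity correction):

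| Share of the better-worn type | Gap | Unadjusted | Stratified |
|---|---|---|---|
| 50% | 0 | 80.4% | 79.7% |
| 50% | 20 points | 80.3% | 81.5% |
| 50% | 40 points | 80.3% | 87.4% |
| 30% | 0 | 80.3% | 79.7% |
| 30% | 20 points | 80.3% | 81.1% |
| 30% | 30 points | 80.4% | 83.2% |

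A 40-point gap with a 30% share would need more than 100% proper wear in the tape arm, so it is omitted. The stratified test's type I error stayed at 4.9% to 5.1%.

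**The case against.** The strongest reply is that the unadjusted chi-square test already allows for chance imbalance. Its error rate holds over repeated randomisations, and a shift of 2 to 4 points is less than half a standard error, in either direction. This stands. A reader might infer that the primary result is biased or its type I error uncontrolled; the documents do not support that. What remains is how the realised result is read, and the precision given up.

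A reader might also infer that baseline significance tests were certainly run. The text assigns the named tests to outcomes. The Wilcoxon test has no outcome to apply to, so its use on age and comorbidity index is a fair inference, but only an inference. A descriptive table would show an imbalance whatever its p-value. The flagging rates above depend on that inference. So does the figure of 1 − 0.95⁷ = 30% for at least one false alarm among seven variables, which also assumes independence; age with comorbidity and race with ethnicity are unlikely to be independent.

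Nor should one say that imbalance is usually missed whatever its size. That holds for 10 points or more taken together, not for 20 or more. It is tempting to quote the 36% power of a 58-per-arm test against a 15-point difference, but that concerns a population difference that randomisation rules out.

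Finally, the documents give no mask-type share and no evidence that mask type predicts proper wear. Being the named subgroup does not establish that it does. Simple randomisation is also the least predictable method, a real advantage in an open-label trial where the same researcher sees the patient at consent and at 60 minutes.

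**Conclusion.** The point holds in limited form. The claim that balance is ensured is wrong on the page, whether the baseline comparison was a test or a table, and the primary comparison ignores a factor that was recorded and singled out. If 116 were randomised and 30% to 50% of masks were hospital-provided, about a quarter of such trials would carry a mask-type imbalance of 10 points or more, and a 5% baseline test would pass about four in five of those. The consequence is weaker precision and a realised result that is harder to interpret. It is neither systematic bias nor a meaningful loss of power from unequal arms. The size of any shift depends on the assumed 20 to 40 point gap between mask types.

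**What to change.** For the completed trial, using data already collected:

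- Report the treatment comparison stratified by mask type as recorded at consent, for example a Cochran-Mantel-Haenszel test with a common risk difference and its confidence interval, beside the unadjusted chi-square test. Label it post hoc if it is added after the data were seen.
- Delete the statement that the comparison ensures balance. Present baseline data as counts and medians by arm, and let no baseline p-value decide any analysis.

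The cost is a little more analysis work and under 1 point of power if mask type does not predict the outcome. The gain is about 1 to 7 points of power on the 50% v 75% contrast if mask types differ by 20 to 40 points (assumption).

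Enrolment ended in October 2020, so allocation cannot be changed. In a repeat trial, restricted randomisation within mask type would limit the imbalance. One example is to toss a coin unless the arms in a stratum differ by 4, then assign the smaller arm. Its price is partial predictability: someone tracking allocations would guess the next one about 56% of the time instead of 50%. In an open-label setting that trade-off has to be weighed.

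### Does naming only significance tests, with no risk difference, confidence interval or mask-type adjustment, leave the primary analysis deficient?

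*Combined protocol and SAP*

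**What the plan says.** The Outcomes section defines one primary endpoint: "The primary outcome of this trial was proper mask utilization at 60 minutes assessed by a researcher". It is binary.

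The Analysis section covers between-group testing in one sentence: "To test for differences between groups on outcomes, Microsoft Excel (Microsoft Corporation, Redmond, WA) was used, and the Chi-square test" (Fisher's exact test where counts are below five) "was used for categorical variables and the Wilcoxon test for continuous variables". Analysis is by intention-to-treat. No risk difference, risk ratio, odds ratio or confidence interval appears anywhere, and neither does any statement that results are given as p-values only.

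The Sample Size section plans on a two-sided chi-square test at the 0.05 level with 50% proper use in controls, and states that "58 participants per arm were needed to have 80% power to detect a 25% relative difference in proper mask adherence".

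On mask type, the Measurements section says "At time of consent, a researcher assessed participants for their mask type, age, gender, race, ethnicity". Consent came before allocation, so mask type is a genuine baseline variable. Allocation was not stratified: "The randomization sequence was generated by a computerized random number generator (simple randomization"). The only stated use of mask type in an outcome analysis is in the Outcomes section: "A subgroup analysis was performed comparing the frequency of correct mask wearing by mask type". Baseline data are handled as follows: "Patient demographics and characteristics were compared between the control and treatment groups (self-reported) to ensure balance after randomization".

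**The concern.** A test says whether the arms differ by more than chance would explain. It does not say by how much, or which effects the data rule out. With 58 per arm the second question matters more than usual. A significant result may be compatible with an effect close to zero, and a non-significant one with an effect as large as the trial was sized to find. A report giving only p-values would hide both.

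The sample-size wording adds to this. A 25% relative increase on 50% is 62.5%, whereas 58 per arm fits 75%. An interval would show where the data stand against either reading.

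Mask type is a second apparent omission. It was known before allocation, it is the only baseline variable singled out for a subgroup analysis, and simple randomisation can leave the arms with different mixes. If hospital-provided and patient-supplied masks differ in how well they stay in place, an unadjusted comparison forgoes some precision. Finally, comparing baseline characteristics after allocation describes balance; it cannot secure it.

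**Working it through.** **Inputs from the document:** 58 per arm, 50% proper use in controls, two-sided 0.05, chi-square test (Sample Size). **Assumptions not in the document:** the mask-type mix and the difference in correct wearing between mask types (the gap). Both are varied below.

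**1. The plan's own figure.** n = [1.96·√(2p̄q̄) + 0.8416·√(p₁q₁ + p₂q₂)]² / (p₂ − p₁)².
- 50% vs 75%: (1.3419 + 0.5567)² / 0.0625 = 57.7, so 58 per arm, with power 80.2%.
- 50% vs 62.5%: (1.3750 + 0.5857)² / 0.015625 = 246.1, so 247 per arm; 58 per arm gives about 27% power.

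The figure of 58 therefore rests on an uncorrected two-sided chi-square test and a 25-point difference. The planned test is the one the trial was sized for. The relative/absolute wording is a separate matter and does not affect which test is used.

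**2. Validity of the test.** Summing over all possible outcomes with 58 per arm and 50% in both arms, the chi-square test rejects in 5.1% of trials.

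**3. What an interval would add.** Half-width = 1.96·√[(p₁q₁ + p₂q₂)/58].
- 50% vs 75%: 1.96·√(0.4375/58) = 17.0 points.
- 50% vs 62.5%: 1.96·√(0.4844/58) = 17.9 points.

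Illustrative results, controls 29/58:

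| Tape arm | Difference (points) | p | Wald 95% CI | Newcombe 95% CI |
|---|---|---|---|---|
| 40/58 | 19.0 | 0.037 | 1.4 to 36.5 | 1.1 to 35.2 |
| 36/58 | 12.1 | 0.19 | −5.9 to 30.0 | −5.8 to 28.9 |

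By the same exact summation, 72.8% of trials are non-significant if the truth is 50% vs 62.5%, and the interval still reaches 25 points in 61% of those (Wald) or 59% (Newcombe). For 50% vs 75% the figures are 20.1% non-significant, of which 88% (Wald) or 86% (Newcombe) reach 25 points.

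The interval is therefore informative. But each one in the table was computed from nothing more than the two numerators and the two denominators, which anyone running the chi-square test already has.

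**4. What mask type could add.** Let a share q wear one mask type, with gap g in both arms and a constant risk difference. Stratifying then removes q(1 − q)g² from each arm's variance. The proportional reduction is 2q(1 − q)g² / (p₁q₁ + p₂q₂). For 50% vs 75% and q = 0.5:
- g = 10 points: 0.005/0.4375 = 1.1%
- g = 20 points: 0.020/0.4375 = 4.6%
- g = 30 points: 0.045/0.4375 = 10.3% (6.6% at an 80/20 mix)

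Simulation with 116 participants, simple randomisation and a 50/50 mix compared the Pearson chi-square with the Cochran–Mantel–Haenszel (CMH) test:

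| Gap (points) | Power change, 50% vs 75% | Power change, 50% vs 62.5% |
|---|---|---|
| 0 | −0.7 | −0.5 |
| 10 | −0.2 | −0.3 |
| 20 | +1.2 | +0.4 |
| 30 | +3.6 | +1.7 |

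Overall type I error was 5.0 to 5.1% for both tests. For 50% vs 75%, the simulated 95% half-width was 17.1 points either way at a 10-point gap, and fell from 17.1 to 16.3 points at a 30-point gap. The table shows what replacing the primary test would do. A supporting stratified estimate would leave primary power exactly where it is.

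**The case for a change.** The strongest case for acting is that it costs almost nothing. Counts, a risk difference and an interval take a few lines and need no new data. A reader cannot rebuild the interval unless counts are reported, and the document does not promise them. With half-widths of 17 to 18 points and an ambiguous design effect, a bare p-value would be easy to misread. Mask type is a legitimate baseline covariate, and one supporting stratified estimate would show whether chance imbalance mattered.

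The first part stands as reporting advice: a paper on this trial should give the counts, the difference and the interval. It does not show a fault in the analysis. The document is a short, past-tense methods summary; silence about the form of reporting is not a decision to withhold estimates.

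The second part is weaker. The document is dated 11/9/2021 and enrolment ran from April to October 2020, so a stratified analysis added now would be post hoc. Its benefit depends on two quantities the document does not supply, and could be nil or slightly negative. One point in its favour is fair: part of the small loss at low gaps comes from CMH using N − 1 where Pearson uses N, so the loss should not be pressed hard. Conditional error rates do not rescue it either. At a 30-point gap the unadjusted rate is 6.9% in the 29% of trials imbalanced by 10 points or more, but 4.4% in the other 71%. The two offset, and the overall rate is nominal.

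**Conclusion.** No change to the plan follows. The primary test is valid, agrees with the sample-size basis, and gives a sound answer if carried out as written. The missing risk difference and interval are a reporting detail that an analyst supplies from the two-by-two table. Their absence alters no design feature, data item or primary conclusion, although the interval itself (about ±17 to 18 points at the planned size) is well worth printing. The number actually enrolled is not stated, so that width applies to the plan.

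Adjustment for mask type is a fair trade-off left at the simpler choice. With gaps of 10 to 20 points and a 50/50 mix, variance falls by only 1.1 to 4.6%. Even a 30-point gap gives 3.6 points of power, and only if the stratified test became primary, which could not be prespecified at this stage.

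Whether the subgroup sentence means arms within mask type or mask types against each other is a matter of clarification, and the phrase about ensuring balance is loose wording. Neither affects the primary comparison.
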